Appendix D Flags used in the safety PCSA and abnormality analysis

Table 2 - Flags for laboratory parameters

Flags	Definition
B	Baseline value
L	Value < LLN
H	Value > ULN
-	Value reaching the lower PCSA limit of the list
--	Value reaching the second lower PCSA limit^a
+	Value reaching the upper PCSA limit of the list
++	Value reaching the second upper PCSA limit of the list^b
*	Value of ALT ≥ 3 ULN and total bilirubin ≥ 2 ULN
#	Conjugated bilirubin > 35% total bilirubin and total bilirubin > 1.5 ULN

^a applicable to creatinine clearance only for which several potential classes of PCSA are defined (moderate and severe classes are flagged in the same way “-“).

^b for more than 2 upper PCSA limit, “++” flag will be used

Table 3 - Flags for vital signs parameters

Flags	Definition
“B”	Baseline value
“-“	Value reaching the lower PCSA limit of the list
“+”	Value reaching the upper PCSA limit of the list

Table 4 - Flags for ECG

Flags	Definition
"B"	Baseline value
"-"	Value reaching the lower PCSA limit of the list ^a
"+"	Value reaching the upper PCSA limit of the list ^b
"++"	Value reaching the second upper PCSA limit of the list ^c

^a "-" is applicable to HR

^b "+" is applicable to HR, PR, QRS, borderline QTc ([431-450] ms for males or [451-470] ms for females) and borderline delta QTc (delta QTc [30-60] ms).

^c "++" is applicable to prolonged QTc (>450 ms for males or >470 ms for females) and prolonged delta QTc (delta QTc > 60 ms).

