2.7.4 Electrocardiogram

ECG parameters (HR in bpm, QTc, QT, QRS and PR in msec) will be derived from the ECG obtained in hospital or during Visit days as per schedule of events. All parameters will be analyzed as raw data and absolute change from baseline. In addition, for the abnormalities analysis, PR and QRS will be also analyzed as percent change from baseline.

Baseline definition

The values to be used as baselines will be the Day 1 predose assessment values. If any of the scheduled baseline tests are repeated for any subject, the last rechecked values will be considered as baselines, provided they were done before the IMP administration of the respective treatment phase, and in the same condition.

Abnormalities analyses

For all parameters, analysis will be performed, using all post-baseline assessments done during the TEAE period, including all unplanned and rechecked values. Counts of patients with PCSAs will be presented by treatment, regardless of the baseline status.

Descriptive statistics and plots

ECG parameters (raw data and absolute change from baseline) will be summarized in descriptive statistics by treatment and scheduled time of measurement.

Additionally, graphs over time will be presented plotting mean +/- SD by treatment.

Listings

Following listings will be produced, using all data, including rechecked or unplanned values.

- A listing of individual data of subjects with any post-baseline PCSAs will be provided; raw data and absolute or percent change from baseline will be displayed depending on the parameter and values will be flagged when reaching the limits of the PCSA criteria;
- In addition, subjects with QTc/QTcB/QTcF >480 ms and/or change from baseline in QTc/QTcB/QTcF >60 ms will also be listed separately, using all post-dose timepoints.

- A listing of subjects with at least one abnormality in qualitative assessment (ie, abnormal 12-lead ECG) after the 1st dosing will be also provided.

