At least grade 2	>220 ms and increase from baseline $\geq 25\%$	
At least grade 3	>240 ms and increase from baseline $\geq 25\%$	
QRS		
High, all grades	>110 ms	Birth/0 to 27 days old : ≥ 85 ms 28 days/1 month to 23 months old: ≥ 85 ms 24 months/2 years to <6 years old: ≥ 95 ms 6 to <12 years old : ≥ 100 ms 12 to 16/18 years old : ≥ 110 ms
At least grade 1 (adults)	>110 ms	
At least grade 2 (adults)	>120 ms	
High and increase from baseline (adults)		
At least grade 1	>110 ms and increase from baseline $\geq 25\%$	
At least grade 2	>120 ms and increase from baseline $\geq 25\%$	
QTc Fridericia		
Increase from baseline, Grade 1	Increase from baseline [30-60] ms	All age classes: Increase from baseline (30-60] ms
Increase from baseline, Grade 2	Increase from baseline >60 ms	All age classes: Increase from baseline >60 ms

References:

- for adults: Criteria for Potentially Significant Abnormalities – for Phase 2/3 studies (oncology excepted) - Version 3.0 - 21-MAY-2014

- for children: Criteria for Potentially Clinically Significant Abnormalities for Studies in Children - Version 3.0 - 21-MAY-2014

Vital signs parameter	Adults	Children
PCSA criteria n/N1 (%)		
Systolic blood pressure supine		
Low and decrease from baseline	≤95 mmHg and decrease from baseline ≥20 mmHg	Birth/0 to 27 days old : ≤ 60 mmHg and decrease from baseline ≥20 mmHg 28 days/1 month to 23 months old: ≤ 70 mmHg and decrease from baseline ≥20 mmHg 24 months/2 years to <6 years old: ≤ 70 mmHg and decrease from baseline ≥20 mmHg 6 to <12 years old : ≤ 80 mmHg and decrease from baseline ≥20 mmHg 12 to 16/18 years old : ≤ 90 mmHg and decrease from baseline ≥20 mmHg
High and increase from baseline	≥160 mmHg and increase from baseline ≥20 mmHg	Birth/0 to 27 days old : ≥ 85 mmHg and increase from baseline ≥20 mmHg 28 days/1 month to 23 months old: ≥ 98 mmHg and increase from baseline ≥20 mmHg 24 months/2 years to <6 years old: ≥ 101 mmHg and increase from baseline ≥20 mmHg 6 to <12 years old : ≥ 108 mmHg and increase from baseline ≥20 mmHg 12 to 16/18 years old : ≥ 119 mmHg and increase from baseline ≥20 mmHg
Diastolic blood pressure supine		
Low and decrease from baseline	≤45 mmHg and decrease from baseline ≥10 mmHg	Birth/0 to <6 years old : ≤ 34 mmHg and decrease from baseline ≥10 mmHg 6 to <12 years old : ≤ 48 mmHg and decrease from baseline ≥10 mmHg 12 to 16/18 years old : ≤ 54 mmHg and decrease from baseline ≥10 mmHg

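### SAP Appendix C counts QTc abnormalities only by rise from baseline, Appendix D flags absolute QTc limits as if they were in that list, and section 2.7.4 lists at a third absolute limit; the three need one set of limits and a by-arm count.

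*SAP*

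**What the plan says.** Three parts of the SAP set QTc limits.

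- **Appendix C, ECG criteria (adults).** QTc Fridericia has a grade 1 row, "Increase from baseline [30-60] ms", and a grade 2 row, "Increase from baseline >60 ms". There is no absolute QTc row. Heart rate, PR and QRS each have rows on the absolute value alone, and further rows that require both a limit and a change.
- **Appendix D, Table 4.** The `++` flag is defined as "Value reaching the second upper PCSA limit of the list", and `+` likewise as the upper limit. The footnotes then assign `+` to "borderline QTc ([431-450] ms for males or [451-470] ms for females" and `++` to "prolonged QTc (>450 ms for males or >470 ms for females) and prolonged delta QTc". The change limits match Appendix C; the absolute limits do not appear there.
- **Section 2.7.4.** The by-arm abnormality table is specified as: "Counts of patients with PCSAs will be presented by treatment, regardless of the baseline status". Absolute QTc appears only under Listings: "subjects with QTc/QTcB/QTcF >480 ms and/or change from baseline in QTc/QTcB/QTcF >60 ms will also be listed separately".

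The QT correction also differs. Appendix C names Fridericia, Appendix D says only QTc, and section 2.7.4 names QTc, QTcB and QTcF together. Protocol section 14.8.4 gives no QTc limit and also counts only PCSAs by treatment.

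**The concern.** A flag defined as reaching a limit in a list should point to a limit that is in the list. For absolute QTc it does not. Either Appendix C lacks rows that Appendix D presupposes, or Appendix D marks as PCSAs values that are not PCSAs. Two programmers could build different by-arm QTc tables from this SAP and each cite an appendix in support.

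ECG results are among the primary safety endpoints in the protocol's Clinical Trial Summary, and no criterion in protocol sections 8.2 and 8.3 limits QTc at entry, so patients can start with a long interval. For them, a count based only on a rise of at least 30 ms says nothing about how many are at a long absolute QTc on each arm. Adverse event tables are not a dependable substitute, because protocol section 11.3.1 records an ECG abnormality as an AE only under stated conditions (symptoms, treatment or consultation, a change to study product, seriousness, or AESI status).

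**Working it through.** The plan states no figure to reproduce. The check is to apply the three rules literally to hypothetical patients.

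**Rules** (Q = on-treatment QTc, B = baseline, both in ms; rise = Q − B; one correction assumed throughout)

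- Appendix C count: grade 1 if the rise is 30 to 60; grade 2 if the rise is above 60; otherwise none.
- Appendix D flag: `++` if Q is above 450 (men) or 470 (women), or the rise is above 60; otherwise `+` if Q is 431–450 (men) or 451–470 (women), or the rise is 30 to 60.
- Section 2.7.4 listing: yes if Q is above 480 or the rise is above 60.

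| Patient | B to Q | Rise | Appendix C count | Appendix D flag | >480/>60 listing |
|---|---|---|---|---|---|
| Man | 425 to 445 | 20 | none | `+` | no |
| Man | 440 to 465 | 25 | none | `++` | no |
| Man | 455 to 480 | 25 | none | `++` | no |
| Woman | 450 to 479 | 29 | none | `++` | no |
| Man | 480 to 505 | 25 | none | `++` | yes |
| Woman | 491 to 520 | 29 | none | `++` | yes |
| Either sex | 380 to 412 | 32 | grade 1 | `+` | no |
| Man | 440 to 470 | 30 | grade 1 | `++` | no |
| Man | 440 to 505 | 65 | grade 2 | `++` | yes |

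**What the rows show**

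1. The count and the flag diverge in the first six rows. A woman at 520 ms is not counted, while a patient at 412 ms is.
2. Above 480 ms the listing catches the patient whatever the rise (rows 5 and 6).
3. Between the Appendix D prolonged limit and 480 ms, with a rise under 30 ms, neither output catches the patient (rows 2 to 4). For men this band runs from above 450 to 480 ms, a width of 480 − 450 = 30 ms. For women it runs from above 470 to 480 ms, a width of 480 − 470 = 10 ms.
4. If Appendix D's absolute limits were also rows of Appendix C, rows 2 to 6 would be counted as prolonged and row 1 as borderline.

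The same ambiguity reaches the PCSA listing in section 2.7.4: whether the patients in rows 1 to 6 belong in it for QTc depends on which appendix defines a QTc PCSA.

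**The case against.** A reader might infer that a patient with a very long QTc and a small rise disappears from the by-arm output. The documents do not support that. Section 2.7.4 summarises raw QTc by treatment and time point, and section 2.9 includes the maximum, so the value is in the arm's N and bounded by its reported maximum. Every post-dose value above 480 ms is listed, and section 2.9 sorts individual data by treatment group. With 27 patients planned on 400 mg and 27 on placebo (protocol Table 1), such a listing can be read directly. A trace read as abnormal goes into another listing, and the patient may also be counted for heart rate, PR, QRS or a TEAE. All of this stands, and it limits the point to the categorical count of absolute QTc.

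It might also be inferred that the omission is certain. The SAP does not say which appendix governs. The column heading in Appendix C, which marks its rows as counts and percentages, favours Appendix C, but if Appendix D governs then absolute QTc is a PCSA and is counted. What is certain is the conflict.

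Change from baseline is, further, a defensible way to look for a drug effect, and an absolute row will pick up prolongation present before dosing. That is fair, and it is why the fix needs a split by baseline. QT prolongation is also neither an AESI nor an EOSI in this trial (protocol sections 11.2.3 and 11.2.4), which tempers the importance.

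**Conclusion.** The inconsistency between Appendix C, Appendix D and section 2.7.4 is in the text and rests on no outside figure. With Appendix C governing, a patient with a long absolute QTc and a rise under 30 ms enters no by-arm categorical QTc count. A patient above the Appendix D prolonged limit but not above 480 ms, with a rise under 30 ms, is flagged `++` and is in neither that count nor the >480/>60 ms listing.

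How many patients this affects cannot be derived. It depends on the mean, spread and visit-to-visit variation of QTc, none of which the documents give, so any percentage would be an assumption and none is offered. Many such values may already be long at baseline, so the gap should not be read as evidence of a missed drug effect. The point merits correction before database lock: it decides what a by-arm table shows for a primary safety endpoint, but it does not make these patients invisible.

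**What to change.** 1. **Appendix C.** Under QTc Fridericia, add absolute post-baseline rows using limits already in the SAP: 431–450 ms (men) or 451–470 ms (women); above 450 ms (men) or 470 ms (women); and above 480 ms. Keep the two change rows.
2. **Appendix D, Table 4.** Refer to those rows, and say which flag applies above 480 ms. Table 2 already uses `++` where a parameter has more than two upper limits, and the same convention would serve.
3. **Section 2.7.4.** Use the same limits in the listing, and state one QT correction for the counts, flags and listing.
4. **By-arm table.** Present the absolute rows by arm and by baseline QTc category, as an exception to the current rule of ignoring baseline status. SAP section 2.7.2 already counts laboratory PCSAs by baseline status, so there is a precedent.

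Deleting the absolute flags from Appendix D would also remove the contradiction, but would leave no by-arm count of absolute QTc.

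The cost is SAP wording and a few more table rows, many of which may reflect prolongation already present at baseline. The ECGs are already collected, and no visit or procedure changes.
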